**Table 2 Study Drug Dosing Information**

Cohort	Treatment	Volume to Administer/Dose	# Doses	Total Study Drug
A	20 mg ISIS 703802 or placebo (Every week)	0.2 mL	26	520 mg
B	40 mg ISIS 703802 or placebo (Every 4 weeks)	0.4 mL	6	240 mg
C	80 mg ISIS 703802 or placebo (Every 4 weeks)	0.8 mL	6	480 mg

## 8.2 Other Protocol-Required Drugs

No other Study Drug treatments are required by the protocol.

## 8.3 Other Protocol-Required Treatment Procedures

There are no other treatment procedures required by the protocol other than those outlined in the schedule of procedures.

## 8.4 Treatment Precautions

No specific treatment precautions are required.

## 8.5 Safety Monitoring Rules

Please refer also to the “Guidance for Investigator” section of the Investigator’s Brochure.

For the purposes of safety monitoring, Baseline is defined as the average of the pre-dose test closest to Day 1 and the Day 1 value itself.

In addition to the standard monitoring of clinical safety parameters, the following guidelines are provided for the monitoring of selected parameters chosen based on preclinical and clinical observations.

In case of discrepancy between the test results from 2 sources, such as between the central and local lab, safety-mandated action must be initiated based on the more critical (lower or higher, as relevant) of the 2 values.

**Confirmation Guidance:** At any time during the study (treatment or post-treatment follow-up periods), the clinical laboratory results meeting any of the safety monitoring criteria presented below **must be confirmed** by performing measurements (ideally in the same laboratory that performed the initial measurement) on new specimens prior to administering the next dose of Study Drug (ISIS 703802 or placebo). All new specimen collections should take place as soon as possible (ideally within 3 days of the initial collection).

In addition, as described in [Section 6.2](#) hematology labs should be sent in parallel to the central and local laboratory for analysis.

**Stopping Rule Guidance:** The Investigator may interrupt or permanently discontinue study treatment for any medical reason including changes in clinical laboratory results.

In the event of an initial clinical laboratory result that meets a stopping criterion, subjects must not be re-dosed until a confirmatory test result has been reviewed by the Study Medical Monitor. If any of the stopping criteria described below are met and are confirmed, the subject will be permanently discontinued from further treatment with Study Drug (ISIS 703802 or placebo), evaluated fully as outlined below and in consultation with the Study Medical Monitor or appropriately qualified designee, and will be entered into the post-treatment evaluation portion of the study. In general, subjects who do not meet the stopping rules based upon retest may continue dosing. However, the Investigator and the Study Medical Monitor (or appropriately qualified designee) should confer as to whether additional close monitoring of the subject is appropriate.

**Additional Guidance:** If possible, a PK sample should be collected as soon as possible after a SAE has occurred (preferably within 2 weeks). In addition, if a subject is asked to return to the clinic for additional evaluations due to an AE, then a PK sample should be taken at the time of the unscheduled visit.

### **8.5.1 Safety Monitoring Rules for Liver Chemistry Tests**

The following rules are adapted from the FDA guidance for industry, “Drug-Induced Liver Injury: Premarketing Clinical Evaluation,” issued by the U.S. Department of Health and Human Services, Food and Drug Administration, July 2009 and adopted to meet the requirements of this protocol and compound to ensure safety of the subjects.

While on treatment, all subjects will have liver chemistry tests monitored every 2 weeks during the first 3-months of the study treatment period, and monthly thereafter. Upon completion of the study treatment period, liver chemistry tests should be monitored per visit schedule in [Appendix A](#).

In the event of appearance of symptoms or signs of hepatic injury (jaundice, fatigue, nausea, vomiting, right upper quadrant pain or tenderness, fever, rash, abnormal bleeding or bruising, or eosinophilia > ULN) liver enzymes and bilirubin should be tested as soon as possible. Testing at a lab that is local to the subject is permissible for this purpose.

In the event of an ALT or AST measurement that is > 3 x ULN (or the greater of 2 x Baseline value or 3 x ULN if the Baseline value was > ULN) at any time during the study (treatment or post-treatment period), the initial measurement(s) should be confirmed.

Subjects with confirmed ALT or AST levels  $> 3 \times$  ULN should have their liver chemistry tests (ALT, AST, ALP, international normalized ratio [INR] and total bilirubin) retested at least once-weekly until ALT and AST levels become  $\leq 2 \times$  ULN.

All results of liver function tests must be reviewed promptly (within 48 hours of receipt) by the Investigator or the designee to ensure that the result has not met the stopping rules.

Further Investigation into Liver Chemistry Elevations: For subjects with confirmed ALT or AST levels  $> 3 \times$  ULN, the following evaluations should be performed:

1. Obtain a more detailed history of symptoms and prior and concurrent diseases
2. Obtain further history for concomitant drug use (including nonprescription medications, herbal and dietary supplement preparations), alcohol use, recreational drug use, and special diets
3. Obtain a history of exposure to environmental chemical agents and travel
4. Serology for viral hepatitis (hepatitis A virus [HAV] immunoglobulin M [IgM], hepatitis B surface antigen [HBsAg], hepatitis C virus [HCV] antibody, Cytomegalovirus [CMV] IgM, and EBV antibody panel)
5. Serology for autoimmune hepatitis (e.g., antinuclear antibody [ANA])

Additional liver evaluations, including gastroenterology/hepatology consultations, hepatic CT or MRI scans, may be performed at the discretion of the Investigator, in consultation with the Sponsor Medical Monitor. Repetition of the above evaluations should be considered if a subject's ALT and/or AST levels reach  $5 \times$  ULN.

All routine liver function test results will be reviewed on an ongoing basis by the Medical Monitor.

All lab alerts for abnormal liver function tests must be promptly (within 48 hours of receipt) reviewed by the Investigator and Medical Monitors.

Lab alerts for abnormal liver chemistry tests will be issued for: 1) ALT or AST  $> 3 \times$  ULN; 2) ALT or AST  $> 2 \times$  Baseline; 3) total bilirubin  $> \text{ULN}$ ; 4) ALP  $> 1.5 \times$  ULN. These alert levels are set to anticipate the risk of a combined elevation of aminotransferases and bilirubin as per the FDA Guidance.

### **8.5.2 Safety Monitoring for Renal Function**

While on treatment all subjects will have renal function tests monitored every 2 weeks during the first 3 months of the study treatment period, and monthly thereafter. Upon completion of the study treatment period, urine renal biomarkers should be monitored as per visit schedule in [Appendix A](#).

In the event of appearance of symptoms or signs consistent with renal dysfunction such as hematuria, polyuria, anuria, flank pain, new-onset hypertension, nausea and/or anorexia, renal function should be tested as soon as possible. Testing at a lab that is local to the subject is permissible for this purpose.

While on treatment during the course of the study, urinary surveillance may include urinalysis to include urine albumin/creatinine ratio (UACR), urine protein/creatinine ratio (UPCR) and urinary red blood cells (RBCs), as well as serum creatinine and cystatin-C, which will be monitored every 2 weeks during the first 3-months of the study treatment period, and monthly thereafter. In addition, other biomarkers of acute renal injury may also be measured if a safety signal is seen that warrants further testing ([Appendix B](#)).

The assessment of serum creatinine, cystatin-C, and urinalysis more frequently than per the Schedule of Procedures in [Appendix A](#), will be guided by consultation with the medical monitor. Any decision taken by the Investigator to discontinue study medication will be made taking into account all available and relevant data. In addition, the decision to discontinue Study Drug may also be based on lesser changes in these parameters observed in isolation or association with other renal-related abnormalities. Any decision taken to restart study medication will be made in consultation with the Study Medical Monitor taking into account all available and relevant data.

All results of renal function tests must be reviewed promptly (within 48 hours of receipt) by the Investigator or the designee to ensure that the result has not met the stopping rules.

Lab alerts for abnormal renal tests will be issued for: Estimated GFR (eGFR) (by CKD-EPI formula) decrease from Baseline > 25%, urine albumin/creatinine ratio (UACR) > 165 mg/g, urine protein/creatinine ratio (UPCR) > 325mg/g, or an increase in serum creatinine from Baseline > 0.3 mg/dL, or new onset hematuria defined as  $\geq 5$  RBC/hpf (except for menstruating females).

These alert levels are set to anticipate and prevent the risk of a medically significant change in renal function while receiving Study Drug.

Abnormal test results should be repeated. In the event of a confirmed laboratory result meeting one or more of the above criteria, the following supplemental renal tests should be obtained within 7 days, and additional laboratory studies may be performed to identify if other potential etiologies may be a causal factor:

Serum creatinine, urine culture, urine microscopy sample with inspection of sediment.

The Investigator should also review the subject's concomitant medications for potentially nephrotoxic agents, and, with the results of these evaluations, review any decision to continue or discontinue the subject in consultation with the Study Medical Monitor.

### **8.5.3 Safety Monitoring for Platelet Count Results**

All subjects will have platelet counts monitored every 2 weeks for the duration of the study treatment period and must not receive Study Drug without an interpretable platelet count result in the prior 2 weeks. Upon completion of the study treatment period, platelets should be monitored every 2 weeks for the first 6 weeks and then at 8 and 13 weeks post last dose (as per visit schedule).

All platelet count results must be reviewed promptly (within 48 hours of receipt) by the Investigator or the designee to ensure that the count has not met the stopping rule and to

determine whether the rate of decline is suggestive that the subject could be approaching the dose interruption rule of 75,000/mm^3.

Any case of a platelet count reduction to levels below 50,000/mm^3 is considered an adverse event of special interest and should be reported in an expedited fashion to the Sponsor. In this case, the Investigator should refer the subject to a hematologist to provide diagnostic and therapeutic management.

Lab alerts related to platelet monitoring/stopping rules are issued when: 1) platelet counts are < 140,000 mm^3, 2) platelet count is  $\geq$  30% decreased from Baseline, or 3) the hematology sample is unreportable. All lab alerts are reviewed promptly by the Medical Monitor, and instructions are communicated to the Investigator and the study personnel within 24 hours of receiving an actionable lab alert.

Actions to be taken in the event of reduced platelet count are shown in [Table 3](#).

In the event of a platelet count < 100,000/mm^3, the laboratory tests outlined in [Table 3](#) should be performed as soon as possible. In addition to action taken as outlined in [Table 3](#), in the event of a platelet count <100,000/mm^3, tests outlined in [Appendix E](#) should be performed as soon as possible. Additional lab tests, if warranted, will be determined by the Sponsor Medical Monitor or designee in consultation with the Investigator.

#### **8.5.4 Safety Monitoring for Bleeding Events**

Subjects will be evaluated for occurrence of bleeding events continuously after the start of Study Drug treatment (Day 1) up to the end of the follow-up period for all cohorts. All bleeding events are considered adverse events and reported on adverse event case report form.

Bleeding events that are either major or clinically-relevant non-major bleeding (as defined below) will need to be monitored and treated immediately. Subjects with a suspected bleeding event will undergo additional testing if deemed appropriate by the treating physician and an (S)AE case report form will be completed. In addition, if bleeding is considered significant, hemoglobin (Hb), hematocrit (HCT), aPTT, PT, INR, and platelet count are to be obtained. In addition, approximately 2 mL of K2EDTA anticoagulated blood will be collected and resulting plasma must be stored allowing for a centralized assessment of ISIS 703802 concentrations.

In addition, if a minor bleeding event occurs, the Investigator should notify the Sponsor Medical Monitor (or designee) and additional testing of coagulation parameters (aPTT, prothrombin time [PT], INR), platelet count, and platelet volume may be performed.

#### *Definitions:*

Major bleeding (MB) is defined as one of the following ([Büller et al. 2007](#)):

1. Fatal bleeding
2. Symptomatic bleeding in a critical area or organ, such as intracranial, intraspinal, intraocular, retroperitoneal, intraarticular if in a major joint, or pericardial, or intramuscular with compartment syndrome

3. Clinically overt bleeding leading to transfusion of  $\geq 2$  units of packed red blood cells or whole blood or a fall in hemoglobin of 20 g/L (1.24 mmol/L) or more within 24 hours

Clinically-relevant non-major bleeding is defined as overt bleeding not meeting the criteria for major bleeding, but that resulted, for example, in medical examination, intervention, or had clinical consequences for a subject (Büller et al. 2007).

Minor bleeding events are those that do not fulfill the criteria for major bleeding or clinically-relevant, non-major bleeding events (defined above), for example, excess bruising, petechiae, gingival bleeding on brushing teeth.

#### **8.5.5 Safety Monitoring for Constitutional Symptoms**

Subjects will be instructed to promptly report any signs or symptoms of fever, constitutional symptoms, rash, arthralgia or joint swelling that may arise during the study and the Investigator should closely evaluate all potential causes, including concomitant illness. Subjects who experience persistent symptoms should be discussed with the Sponsor Medical Monitor or designee to determine whether additional monitoring or laboratory tests are required.

#### **8.5.6 Safety Monitoring for Hypoglycemia**

Subjects will be instructed to monitor and manage hypoglycemic episodes. Subjects will be provided with a glucometer and asked to record Self Monitored Blood Glucose (SMBG) levels weekly and report back alert values to the site. Subjects will be instructed to promptly report symptoms of hypoglycemia: headache, heart pounding, confusion, disorientation, numbness or tingling, pale skin, shakiness or tremulousness, increased appetite, anxiousness or nervousness, lightheadedness or dizziness, sweating and, weakness. If subjects suspect they might be having a hypoglycemia reaction, they should check their blood glucose using their meters as soon as possible, before treatment if possible, provided they feel it is safe to do so. If there is doubt about safety they should treat the event first, using some sugar, milk, or juice for example, then obtain and record a blood glucose value as soon as possible thereafter. The time and nature of treatment should be noted, and especially if any blood glucose result was before or after treatment. If a subject presents with symptoms of hypoglycemia, the Investigator will need to take immediate action to confirm the subject's glucose level and treat the subject accordingly. Severe hypoglycemia will be qualified as a SAE only if it fulfills SAE criteria.

#### ***Classification of Hypoglycemia***

The alert value for hypoglycemia is  $\leq 70$  mg/dL ( $\leq 3.9$  mmol/L) blood glucose concentration.

#### ***Severe Hypoglycemia***

Requires assistance of another person to actively administer carbohydrates, glucagon, or take other corrective actions. Glucose concentrations may not be available during an event. Neurological recovery following glucose levels returning to normal considered sufficient evidence that event was induced by low glucose concentration.

### *Documented Symptomatic Hypoglycemia*

Typical hypoglycemia symptoms accompanied by measured blood glucose  $\leq 70$  mg/dL ( $\leq 3.9$  mmol/L).

### *Asymptomatic Hypoglycemia*

Not accompanied by typical hypoglycemia symptoms but with measured blood glucose  $\leq 70$  mg/dL ( $\leq 3.9$  mmol/L).

### *Probable Symptomatic Hypoglycemia*

Typical hypoglycemia symptoms not accompanied by blood glucose determination but likely caused by blood glucose  $\leq 70$  mg/dL ( $\leq 3.9$  mmol/L).

A **documented severe hypoglycemic event** is defined as one in which the subject requires the assistance of another person to obtain treatment for the event and has a blood glucose level  $\leq 70$  mg/dL ( $\leq 3.9$  mmol/L). The rescue treatment of hypoglycemia may include IV glucose or buccal or intramuscular glucagon.

The definition of severe symptomatic hypoglycemia includes all episodes in which neurological impairment was severe enough to prevent self-treatment and which were thus thought to place subjects at risk for injury to themselves or others.

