#### **8.6.4 Stopping Rule for Documented Severe Hypoglycemia**

In the event of a first instance of documented severe hypoglycemia, dosing of a subject with Study Drug will be suspended temporarily. The need to adjust the background medication and the suitability of the subject for continued dosing will be determined by the Investigator in consultation with the Study Medical Monitor. In the event of a second instance of documented severe hypoglycemia, after a re-challenge, dosing of a subject with Study Drug will be stopped permanently.

Dose adjustments, including dose interruptions, and/or decreasing the dose or dose frequency will be allowed for safety and tolerability. **Any proposed adjustments to treatment schedule must be discussed with, and approved by, the Study Medical monitor prior to initiation.**

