#### **9.4.3 Evaluation of Adverse Events (Serious and Non-Serious)**

The Investigator's opinion of the following should be documented on the Adverse Event Case Report Form.

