#### 9.4.3.2 *Severity*

The severity of AEs and SAEs will be graded based on criteria from the Common Terminology Criteria for Adverse Events (CTCAE) Version 4.03, June 2010 (refer to [Appendix D](#)). Any AE not listed in [Appendix D](#) will be graded as follows:

- **Mild:** The event is easily tolerated by the subject and does not affect the subject's usual daily activities
- **Moderate:** The event causes the subject more discomfort and interrupts the subject's usual daily activities
- **Severe:** The event is incapacitating and causes considerable interference with the subject's usual daily activities

If the event is an SAE, then all applicable seriousness criteria must be indicated (criteria listed in [Section 9.3.3](#)).

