## **Appendix D      Grading Scale for Adverse Events Relating to Laboratory Abnormalities**

## Appendix D Grading Scale for Adverse Events Relating to Laboratory Abnormalities

The following grading recommendations for adverse events relating to lab test abnormalities are based upon the Common Terminology Criteria for Adverse Events (CTCAE) Version 4.03, June 2010.

Adverse Event	Mild	Moderate	Severe
Hematology			
aPTT prolonged	>ULN - 1.5 x ULN	>1.5 - 2.5 x ULN	>2.5 x ULN; hemorrhage
Eosinophils increased f	650 – 1,500 cell/mm 	1,501 - 5,000 cell/mm 	>5,000 cell/mm 
Fibrinogen decreased	<1.0 - 0.75 x LLN or <25% decrease from baseline	<0.75 - 0.5 x LLN or 25 - <50% decrease from baseline	<0.5 x LLN or ≥50% decrease from baseline
Hemoglobin decreased (Anemia)	Hemoglobin (Hgb) <LLN - 10.0 g/dL; <LLN - 6.2 mmol/L; <LLN - 100 g/L	Hgb <10.0 - 8.0 g/dL; <6.2 - 4.9 mmol/L; <100 - 80g/L	Hgb <8.0 g/dL; <4.9 mmol/L; <80 g/L; transfusion indicated
Hemoglobin increased	Increase in >0 - 2 g/dL above ULN or above baseline if baseline is above ULN	Increase in >2 - 4 g/dL above ULN or above baseline if baseline is above ULN	Increase in >4 g/dL above ULN or above baseline if baseline is above ULN
INR increased	>1 - 1.5 x ULN; >1 - 1.5 times above baseline if on anticoagulation	>1.5 - 2.5 x ULN; >1.5 - 2.5 times above baseline if on anticoagulation	>2.5 x ULN; >2.5 times above baseline if on anticoagulation
Lymphocyte count decreased	<LLN - 800/mm  ; <LLN - 0.8 x 10  /L	<800 - 500/mm  ; <0.8 - 0.5 x 10  /L	<500 /mm  ; <0.5 x 10  /L
Lymphocyte count increased	-	>4000/mm  - 20,000/mm 	>20,000/mm 
Neutrophil count decreased	<LLN - 1500/mm  ; <LLN - 1.5 x 10  /L	<1500 - 1000/mm  ; <1.5 - 1.0 x 10  /L	<1000/mm  ; <1.0 x 10  /L
Platelet count decreased	<LLN - 75,000/mm  ; <LLN - 75.0 x 10  /L	<75,000 - 50,000/mm  ; <75.0 - 50.0 x 10  /L	<50,000/mm  ; <50.0 x 10  /L
White blood cell decreased	<LLN - 3000/mm  ; <LLN - 3.0 x 10  /L	<3000 - 2000/mm  ; <3.0 - 2.0 x 10  /L	<2000/mm  ; <2.0 x 10  /L
Chemistry			
Acidosis	pH <normal, but ≥7.3	-	pH <7.3

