**Appendix D Grading Scale for Adverse Events Relating to Laboratory Abnormalities**  
*Continued*

Adverse Event	Mild	Moderate	Severe
Cardiac troponin T increased	Levels above the upper limit of normal and below the level of myocardial infarction as defined by the manufacturer	-	Levels consistent with myocardial infarction as defined by the manufacturer
CD4 lymphocytes decreased	<LLN - 500/mm  ; <LLN - 0.5 x 10  /L	<500 - 200/mm  ; <0.5 - 0.2 x 10  /L	<200/mm  ; <0.2 x 10  /L
CPK increased*	>ULN - <6 ULN	6 - 10 x ULN	>10 x ULN
Creatinine increased	>1 - 1.5 x baseline; >ULN - 1.5 x ULN	>1.5 - 3.0 x baseline; >1.5 - 3.0 x ULN	>3.0 x baseline; >3.0 x ULN
GGT increased	>ULN - 2.5 x ULN	>2.5 - 5.0 x ULN	>5.0 x ULN
Hypercalcemia	Corrected serum calcium of >ULN - 11.5 mg/dL; >ULN - 2.9 mmol/L; Ionized calcium >ULN - 1.5 mmol/L	Corrected serum calcium of >11.5 - 12.5 mg/dL; >2.9 - 3.1 mmol/L; Ionized calcium >1.5 - 1.6 mmol/L; symptomatic	Corrected serum calcium of >12.5 mg/dL; >3.1 mmol/L; Ionized calcium >1.6 mmol/L; hospitalization indicated
Hyperglycemia	Fasting glucose value >ULN - 160 mg/dL; Fasting glucose value >ULN - 8.9 mmol/L	Fasting glucose value >160 - 250 mg/dL; Fasting glucose value >8.9 - 13.9 mmol/L	>250 mg/dL; >13.9 mmol/L; hospitalization indicated
Hyperkalemia	>ULN - 5.5 mmol/L	>5.5 - 6.0 mmol/L	>6.0; hospitalization indicated
Hypermagnesemia	>ULN - 3.0 mg/dL; >ULN - 1.23 mmol/L	-	>3.0 mg/dL; >1.23 mmol/L
Hypernatremia	>ULN - 150 mmol/L	>150 - 155 mmol/L	>155 mmol/L; hospitalization indicated
Hyperuricemia	>ULN - 10 mg/dL (0.59 mmol/L) without physiologic consequences	-	>ULN - 10 mg/dL (0.59 mmol/L) with physiologic consequences
Hypoalbuminemia	<LLN - 3 g/dL; <LLN - 30 g/L	<3 - 2 g/dL; <30 - 20 g/L	<2 g/dL; <20 g/L
Hypocalcemia	Corrected serum calcium of <LLN - 8.0 mg/dL; <LLN - 2.0 mmol/L; Ionized calcium <LLN - 1.0 mmol/L	Corrected serum calcium of <8.0 - 7.0 mg/dL; <2.0 - 1.75 mmol/L; Ionized calcium <1.0 - 0.9 mmol/L; symptomatic	Corrected serum calcium of <7.0 mg/dL; <1.75 mmol/L; Ionized calcium <0.9 mmol/L; hospitalization indicated
Hypoglycemia	<LLN - 55 mg/dL; <LLN - 3.0 mmol/L	<55 mg/dL; <3.0 mmol/L	<40 mg/dL (<2.2 mmol/L) AND requires assistance of another person to actively administer carbohydrates, glucagon, or take other corrective actions †

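### Section 8.5.6 defines severe hypoglycaemia by the need for another person's help, but Appendix D also requires glucose below 40 mg/dL, so recommended grades can understate assisted events

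*Protocol*

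**What the plan says.** Three parts of the protocol classify the same kind of event.

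- **Section 8.5.6, Severe Hypoglycemia.** The class rests on help alone, and a missing glucose value is foreseen: "Requires assistance of another person to actively administer carbohydrates, glucagon, or take other corrective actions. Glucose concentrations may not be available during an event". The same section then defines a documented severe event as one in which the subject "requires the assistance of another person to obtain treatment for the event and has a blood glucose level" of 70 mg/dL or less.
- **Section 8.6.4.** The documented form drives dosing: "In the event of a first instance of documented severe hypoglycemia, dosing of a subject with Study Drug will be suspended temporarily". A second such event after re-challenge stops dosing permanently.
- **Section 9.4.3.2 and Appendix D.** "The severity of AEs and SAEs will be graded based on criteria from the Common Terminology Criteria for Adverse Events", with Appendix D as the reference. A general mild, moderate and severe scale is kept for events that Appendix D does not list. Hypoglycaemia is listed: Mild from below the lower limit of normal (LLN) to 55 mg/dL, Moderate below 55 mg/dL, and Severe below 40 mg/dL "AND requires assistance of another person to actively administer carbohydrates, glucagon, or take other corrective actions".

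SAP Section 3.5.1 tabulates treatment-emergent adverse events by severity, counting each patient once at the worst reported grade. It plans no table by the 8.5.6 classes.

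**The concern.** The Severe cell of Appendix D and the severe class of Section 8.5.6 share the same help criterion, yet the cell joins it to a glucose limit that the class does not have. The two texts use one word for different sets of events, and the protocol does not explain the difference.

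What is at stake is how the safety tables read. Safety and tolerability is a secondary objective, and the protocol synopsis makes safety part of dose selection. The drug is expected to improve glycaemic control, and background sulfonylureas are allowed. An assisted event could reach the severity tables as Moderate or Mild although the protocol's own definition calls it severe. Two investigators could also grade the same event differently, each with support in the protocol.

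**Working it through.** The plan gives no figure to reproduce. The check applies each set of cut-offs to an event in which another person had to help.

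| Glucose (mg/dL) | Section 8.5.6 | Section 8.6.4, first event | Appendix D grade |
|---|---|---|---|
| <40 | documented severe | suspend dosing | Severe |
| 40 to <55 | documented severe | suspend dosing | Moderate |
| 55 to below LLN, up to 70 | documented severe | suspend dosing | Mild |
| LLN to 70, if LLN is 70 or less | documented severe | suspend dosing | none given |
| no reading | severe, not documented | not triggered | no clear grade |

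At 70 mg/dL or less, the two texts agree only in the first row.

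**Dependence on the LLN.** The Moderate band does not depend on it. In whole numbers it runs from 40 to 54, which is 54 − 40 + 1 = 15 values. The range 55 to 70 (70 − 55 + 1 = 16 values) does depend on it, and the documents give no LLN. Under three assumed limits:

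- LLN 74: Mild at 55–70 (16 values), none ungraded.
- LLN 70: Mild at 55–69 (15 values), ungraded at 70 (1 value).
- LLN 65: Mild at 55–64 (10 values), ungraded at 65–70 (6 values).

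These counts describe the cut-offs. They say nothing about how often such events occur.

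**Scale.** The planned active groups and the pooled placebo group each have 24 patients. One patient moved out of Severe changes that group's percentage by 1/24 = 4.2 points. The documents give no rate of assisted hypoglycaemia. Few events are to be expected, since insulin is excluded.

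**Where the events remain visible.** SAP Section 3.5.2 tabulates patients who meet a monitoring or stopping rule, citing protocol Section 8.6, which contains the hypoglycaemia rule. The adverse event overview in SAP Section 3.5.1 includes events leading to treatment interruption. Documented severe events should therefore appear in both. An assisted event without a reading does not trigger Section 8.6.4, and it reaches the serious-event tables only under a further condition: "Severe hypoglycemia will be qualified as a SAE only if it fulfills SAE criteria".

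**The case against.** The best reply is that severity grades and dosing rules serve different purposes. A reader might infer that suspending dosing for an event graded below Severe is itself an error. The documents do not support that. Platelets at 50,000 to <75,000/mm³ pause dosing under Table 3 and are Moderate in Appendix D. Confirmed new haematuria without another explanation stops dosing permanently under Section 8.6.2, yet is Mild in Appendix D if asymptomatic. This part of the reply stands. The mismatch lies in the definition of severe, not in the link to dosing.

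Second, the lower grade is not certain. Appendix D introduces its entries in these terms: "The following grading recommendations for adverse events relating to lab test abnormalities are based upon the Common Terminology Criteria for Adverse Events". Section 9.4.3 adds that the investigator's "opinion of the following should be documented on the Adverse Event Case Report Form". An investigator may record Severe. This also stands, so the claim is only that the tables may understate.

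Third, a reader might infer that an assisted event with no reading can never be graded Severe. That goes too far. Appendix D is confined to adverse events relating to laboratory abnormalities, and an event with no measurement could arguably go to the general scale, where an incapacitating event is Severe. Because hypoglycaemia is listed by name, the point is unsettled either way.

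Fourth, a footnote to Appendix D says that an entry was modified to agree with diabetes-society guidance, and by subject this is probably the hypoglycaemia row. The footnote marks are unclear in the extracted text. Even so, the note neither explains nor removes the difference from Section 8.5.6.

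Finally, listings, narratives for significant events and the instruction to obtain a reading as soon as possible all shrink the gap. They do not make the severity tables match the protocol's definition.

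**Conclusion.** The inconsistency is real and minor. For assisted events, Appendix D recommends Moderate at 40 to <55 mg/dL whatever the LLN, and Mild from 55 mg/dL to below the LLN, where Section 8.5.6 says severe. Any understatement depends on investigators following the recommendation and on such events occurring, neither of which the documents quantify. It would be confined to the adverse event severity tables: dosing actions, the stopping-rule counts and the primary efficacy analysis do not use the Appendix D grade. This is a wording repair worth making, not a threat to the trial's conclusions.

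**What to change.** **Preferred.** In the Severe cell of Appendix D for hypoglycaemia, delete the 40 mg/dL condition and keep the help criterion. State that it applies whatever the glucose value and also when there is no reading. This is a one-cell change, but it is a protocol amendment, and Section 12.1 requires the regulatory authority and ethics committee to be informed. Any assisted events already recorded may need review.

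**If no amendment is wanted.** Leave investigator-reported severity as it stands. Recoding it to Severe in the analysis would override the investigator's recorded opinion. Instead, add to the SAP, before unblinding, a separate count by treatment group of patients with events meeting the 8.5.6 severe and documented severe definitions. The cost is one extra table.

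The documents do not say whether the eCRF records that help was needed. If it does not, either route needs one added field.
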